#### **17.6.5 Data Safety Monitoring Board**

A data safety monitoring board (DSMB) will be convened for the safety oversight of the study in order to assure safety of the trial participants.

The DSMB meetings to review the safety data, will be planned after 25%, 50% and 75% or when approximately 70, 135, 230 and 345 randomized patients, respectively, have reached Day 14.

Assessments will include but not be limited to:

- a) all adverse events
- b) all dose reductions in study drug

Ad hoc DSMB meetings will convene when clinically significant events (adverse events of special interest Section 17.6.3), per physician discretion, may indicate a potential increase in systemically important inflammation in any one patient in the study, based on an increased and clinically significant oxygen requirement, or a precipitous clinical deterioration that leads to intubation and mechanical ventilation.

At each review/meeting the DSMB will determine whether the study should proceed as planned or should be terminated.

No formal efficacy analysis (early stopping for efficacy) will be performed at any DSMB review.

An interim analysis to determine futility will be conducted by an independent statistician and reported to the DSMB. The DSMB will also be responsible for conveying the results of the futility analysis conducted by an independent unblinded statistician to the sponsor (futile/non-futile).

A DSMB charter will be provided as a separate document.

## 18 ETHICS

### 18.1 Investigator Responsibilities

#### 18.1.1 Compliance with Declaration of Helsinki and Good Clinical Practices

The study will be performed in accordance with the Declaration of Helsinki (1964) as revised, most recently in Seoul (2008), US FDA regulations and the ICH Guideline for Good Clinical Practice, E6(R1). The investigator will ensure that all those concerned with conducting the study (such as pharmacists, research nurses and co-investigators) are provided with copies of the protocol and all safety information prior to the start of the study.

#### 18.1.2 Institutional Review Board (IRB)/Ethics Committee (EC) Review and Approval

The investigator is responsible for obtaining IRB/EC approval to conduct this study (including IRB/EC approval of the Informed Consent form) and for ensuring continuing review as required by the IRB/EC. Written confirmation of this approval and periodic review must be provided to the sponsor prior to the start of the study and at appropriate intervals.

#### 18.1.3 Informed Consent

The investigator will inform patients as to the nature, expected duration and purpose of the study, the administration of the study medication, and the hazards involved, as well as the potential benefits that may come from treatment with this investigational drug. Informed consent must be obtained in accordance with US Code of Federal Regulations (21 CFR Part 50), and other national regulations, if study is conducted at sites outside the US.

The patient will be informed that his/her medical records will be subject to review by the sponsor and possibly by a representative of the Food and Drug Administration, as well as national regulatory authorities, for patients treated outside the US. Subjects will be informed that they are free to refuse participation in this clinical investigation, and if they should participate, it will be made clear to them that they may withdraw from this study at any time without prejudicing further care. Signed written informed consent must be obtained from every patient or legal representative prior to study entry. The original will be kept by the investigator and will be subject to review by the sponsor; a copy will be given to the patient.

#### 18.1.4 Patient Anonymity

The anonymity of participating patients must be maintained. Patients will be identified by a pseudonymization of patient initials and an assigned patient number on the datasheet, and other documents submitted to the sponsor, including but not limited to safety reports. Documents that will not be submitted to the sponsor and that identify the patient (e.g., the signed informed consent document), must be maintained in strict confidence by the Investigator, except to the extent necessary

to allow auditing by the appropriate regulatory authority, the study monitor, or sponsor representatives.

### **18.1.5 Confidentiality**

All information provided to the investigator relevant to the study medication, as well as information obtained during the course of the study, will be regarded as confidential. The investigator and members of his/her research team agree not to disclose or publish such information in any way to any third-party without prior written permission from the sponsor, except as required by law.

### **18.1.6 Source Documentation**

The investigator will allow inspections of the study site and documentation by clinical research and audit personnel from the sponsor, external auditors or representatives of regulatory authorities. The purpose of these inspections is to verify and corroborate the data collected on the case report forms. In order to do this direct access to the subjects' medical or clinic records is necessary. The investigator will ensure that certain information is contained in the medical or clinic records of the subject and that the entries are signed and dated, as follows:

- sufficient data to allow verification of the entry criteria in terms of past and present medical and medication histories
- a note on the day the subject entered the study describing the study number, the drug being evaluated, the study number assigned to that subject and a statement that consent was obtained
- a note of each subsequent study visit including any concerns about adverse events or abnormal laboratory data and their resolution
- notes of all concomitant medication taken by the subject including start and stop dates
- a note of when the subject terminated from the study, the reason for termination and the subject's general condition at termination
  - a copy of the signed informed consent form should be kept in the medical records of each subject during the clinical phase of the study (thereafter it will be archived with the study file)

### **18.1.7 Drug Accountability**

The investigator agrees to supervise the maintenance of records of the receipt, dispensing and return or destruction of study material supplied by the sponsor. Destruction of any material must be witnessed and documented in writing. The dispensing record must make it clear which subject received which material.

### **18.1.8 Data Monitoring and Collection**

Suitably qualified and trained clinical research personnel of the sponsor will visit the study center at regular intervals during the study for monitoring purposes and to assist the research staff with any queries they may have.

### **18.1.9 Case Report Forms, Investigator's Study File and Record Retention**

All case report forms and supporting source documentation must be available to the sponsor during monitoring visits.

Prior to review of the case report forms by the sponsor's representative and forwarding of the case report forms to the sponsor, they should be reviewed for completeness and legibility by the investigator or a member of the research team.

The investigator will maintain all records relating to the study (including copies of case report forms) for at least 2 years after written notification by the sponsor that the investigational drug program has been either completed or terminated, or that a New Drug Application (NDA) has been approved by the FDA. Should the investigator retire, relocate, or for other reasons withdraw from the responsibility of keeping the study records, custody must be transferred to a person who will accept that responsibility, and the sponsor must be notified in writing of the name and address of said person.

### **18.1.10 Non-Protocol Research**

No investigational procedures other than those outlined in this protocol may be undertaken on the subjects in this study without the prior written permission of the subject, the sponsor and the IRB.

## **18.2 Sponsor Responsibilities**

### **18.2.1 General**

The sponsor agrees to adhere to US FDA Guidelines on Good Clinical (Research) Practices and with the ICH Guideline for Good Clinical Practice, E6(R1). The sponsor has a legal responsibility to report fully to regulatory authorities the results of this study. It is the sponsor's responsibility to obtain appropriate regulatory approval to perform the study.

### **18.2.2 Case Report Forms**

Case report forms will be provided by the sponsor or, upon agreement with the sponsor, forms generated by the investigative site may be used. If an electronic data collection system is used, the system will be compliant with applicable aspects of 21 CFR Part 11, ICH guidelines, GCP and HIPAA.

### **18.2.3 Data Monitoring and Collection**

Suitably qualified and trained clinical research personnel of the sponsor will visit the study center at regular intervals during the study for monitoring purposes and to assist the research staff with any queries they may have. Case report forms and source documentation will be available for review during monitoring visits to the center. The function of this monitoring is to ensure compliance with the protocol, adherence to regulatory and good clinical (research) practice obligations, proper maintenance of records including drug accountability records, correct administration of study medications including storage conditions and accurate reporting of adverse events.

#### **18.2.4 Audit**

The sponsor has an obligation to audit a proportion of studies; this is usually undertaken by a department other than the clinical research department. Therefore the sponsor, an independent auditor or a regulatory authority may wish to audit the study site and documentation and these audits may take place as the study is running or up to several years later.

#### **18.2.5 Confidentiality**

The sponsor will not keep any material on file bearing any subject's name, and the subject's confidentiality will be maintained at all times.

#### **18.2.6 Protocol Modifications**

If necessary, during the course of the study, the protocol may be modified by the sponsor in consultation with the investigator. Except in the case of modifications to resolve an imminent safety issue, any protocol modification or revision must be reviewed and approved by the investigator's IRB/EC prior to implementation.

#### **18.2.7 Publication**

RedHill Biopharma will provide unblinded data to a publications committee for publication of the results of this study once completed and all data have been cleaned and the blind broken. The publications committee will be constituted according to the guidelines developed by the Company. If deemed necessary by the Company for protection of proprietary information prior to patent filing, the investigator agrees to delay for 60 days before any presentation or publication is submitted.

## 19 STATISTICAL METHODS

This section of the protocol describes the statistical analysis as it is foreseen at the time of planning the study. A fully detailed Statistical Analysis Plan (SAP) will be produced and finalized after finalizing the protocol and before breaking the blind of the study. A supplementary document will provide further details regarding the planned futility analysis.

### 19.1 Sample Size Considerations

It is planned to randomize approximately 464 eligible patients into the double-blind treatment phase, to receive either opaganib added to standard of care (n=232), or matching placebo added to standard of care (n=232). The sample size calculation was based on powering the study with respect to the primary analysis of the primary efficacy endpoint of proportions of patients no longer requiring supplemental oxygen for at least 24 hours by Day 14 (refer to Section 15.1). It was assumed that the treatment success rate at 14 days in the control arm would be 40% and that opaganib is expected to provide absolute 15% increase of this rate, to a success rate of 55%. A total of 464 subjects provides 90% power to detect the assumed difference in success rate, using chi square test, at a two-sided  $\alpha=0.05$  level of significance. This sample size calculation takes into account a planned non-binding futility analysis to be performed after at least 135 patients in the study have been evaluated for the primary endpoint.

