### 19.3 Populations for Analysis

The primary analysis will be based on the modified Intent to treat population (mITT), which consists of all patients that were randomized and treated with at least one dose of study drug and who met entry criteria #3 (The patient requires, prior to first dose of study drug, high flow supplemental oxygen or positive pressure ventilation, or is receiving oxygen via a non-rebreather or reservoir mask, capable of delivering high concentrations of oxygen. Patients who require mechanical ventilation or no longer

require supplemental oxygen prior to receiving the first dose of study drug will not be included in the mITT analysis set.

The primary analysis will also be analyzed using a Per-Protocol (PP) population that will be further defined in the SAP and the Intention-to-treat (ITT) population who consists of all randomized patients. In all efficacy analyses, treatment group will be assigned per randomization assignment.

Safety analyses will be based on the safety analysis set, which consists of all patients who received at least one dose of study drug and analyzed based on the actual treatment the subject received.

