## 19.4 Analysis of the Primary Efficacy Endpoint

The primary efficacy endpoint will be based on a success (Yes/No) variable, indicating if a subject is no longer requiring supplemental oxygen, for at least 24 hours by study Day 14 (patient death or subsequent requirement of supplemental oxygen or lost to follow-up through Day 42 will be regarded as a failure for the primary efficacy endpoint). Any subject reported as not requiring supplemental oxygen on any given study day will be counted as a subject who has not required oxygen for at least 24 hours, based on the instructions to sites to enter the highest oxygen requirement for each study day. Subjects who are discharged from hospital on supplemental oxygen are expected to be followed up by the study site daily and will be considered a success only if for any given study day, the highest supplemental oxygen requirement is zero.

If a patient initiates a new investigational therapy on a different formal clinical protocol for COVID-19 within 14 days of randomization, the patient will be followed for true outcomes in the primary analysis but in a sensitivity analysis the data under the new therapy will not be included.

An early discontinuation of study before the subject has reached success (e.g. loss to follow up) thus preventing continued follow-up for success by Day 14, will be considered as missing data and will be counted as failure for the primary analysis. Sensitivity analysis using time to event method will be performed censoring these cases at the latest informative time.

The number and percentages of subjects achieving success (as defined above) will be tabulated per treatment group. A 95% confidence interval will be constructed for each proportion. A Cochran Mantel-Haenzel (CMH) test will compare the proportion of success between the two groups, using the study stratification factors used for randomization, and a corresponding stratified risk difference estimate will be presented with 95% confidence interval.

The significance level for this test will be two-sided 5%.

The primary analysis will be based on the modified Intent to treat population (mITT) as defined in Section 19.3.

Sensitivity and supportive analyses for the primary endpoint analysis will be defined and detailed in the statistical analysis plan. These will address at least the following aspects:

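### Section 19.1 gives 90% power to 464 randomised patients, but the primary analysis is in the smaller mITT set and the number carries no allowance for its exclusions

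*Protocol*

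**What the plan says.** Section 19.1 of the protocol fixes the number randomised: "It is planned to randomize approximately 464 eligible patients into the double-blind treatment phase", 232 per arm. It says the calculation powers the primary analysis of the primary endpoint, with assumed Day 14 success of 40% on placebo and 55% on opaganib. The power claim is "A total of 464 subjects provides 90% power to detect the assumed difference in success rate, using chi square test", at two-sided 0.05. The section closes on the interim look: "This sample size calculation takes into account a planned non-binding futility analysis to be performed after at least 135 patients in the study". The count refers to patients whose primary endpoint is known by then.

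Section 19.3 places the primary analysis in the mITT set, "which consists of all patients that were randomized and treated with at least one dose of study drug", and who also met entry criterion 3 before that dose. Patients who need mechanical ventilation, or no longer need oxygen, before the first dose are left out. Section 12.2 foresees such cases: if changes between randomisation and first dose affect eligibility, the patient should not be treated.

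Section 19.8 requires the primary and all key secondary endpoints to cross before futility can be declared, and leaves the boundaries to the SAP and the DSMB charter.

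**The concern.** The power is stated for a count of randomised patients, while the test is run on a subset of them. If 464 were clearly above the fixed-sample requirement, the difference could absorb both the exclusions and any power lost to the futility look. If it is the fixed-sample requirement with almost nothing added, 90% is reached only when every randomised patient enters the mITT. In this population, oxygen support can change between randomisation and first dose, so some exclusions are to be expected. What is at stake is the accuracy of the stated power of the primary analysis. Type I error is not affected.

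**Working it through.** **Inputs (section 19.1; allocation from 19.2).** p1 = 0.40, p2 = 0.55, difference 0.15, two-sided alpha 0.05 (z = 1.960), power 90% (z = 1.2816), allocation 1:1, chi-square test, 464 randomised.

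**Reproducing the plan's figure.** With the pooled variance under the null hypothesis, mean rate 0.475:

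- n per arm = [1.960·√(2·0.475·0.525) + 1.2816·√(0.40·0.60 + 0.55·0.45)]² / 0.15²
- = [1.960·0.7062 + 1.2816·0.6982]² / 0.0225 = (1.3842 + 0.8948)² / 0.0225 = 230.8

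That is 231 per arm, 462 in total. The arcsine formula gives 231.1, hence 232 per arm. The plan's 464 is thus reproduced by a fixed-sample calculation.

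**Power as a function of the number analysed.** Power = Φ[(0.15·√n − 1.3842) / 0.6982], n per arm:

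| n per arm | Power |
|---|---|
| 230 | 89.9% |
| 231 | 90.0% |
| 232 | 90.1% |

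The margin is 464 − 462 = 2 patients, or 2/464 = 0.4%. With three exclusions the mean is 461/2 = 230.5 per arm and power is just under 90%.

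**Effect of mITT exclusions.** The protocol gives no rate, so 2%, 5% and 10% are assumptions. Exclusions are taken as equal in the two arms, and the rates of 40% and 55% are taken to hold in the mITT.

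| Excluded | n per arm analysed | Power | Randomised needed to keep 462 |
|---|---|---|---|
| 2% | 232 × 0.98 = 227.4 | 89.6% | 472 |
| 5% | 232 × 0.95 = 220.4 | 88.6% | 487 |
| 10% | 232 × 0.90 = 208.8 | 86.9% | 514 |

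The last column is 462/(1 − rate), rounded up. Loss to follow-up is not in this table: section 19.4 counts it as failure, so those patients stay in the denominator.

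**What two patients can buy for futility.** Information fraction 135/464 = 0.291, final critical value kept at 1.96 because the look is non-binding, stopping on the primary alone, all 464 analysed. The boundaries are assumptions.

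| Stop if interim z is below | Power at 464 |
|---|---|
| −1.08 (O'Brien-Fleming-type beta spending; needs 463.2, i.e. 464) | 90.1% |
| −0.9 | 90.0% |
| 0 | 87.9% |
| 0.5 | 83.2% |

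The rule in section 19.8 is more lenient, since all key secondaries must cross as well. With two key secondaries of equal drift and correlations of 0.5, 0.7 and 0.9, simulated power with a boundary at z = 0 is about 90.0%, 89.7% and 89.1%.

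**The case against.** A reader might infer that, because 464 is the fixed-sample number plus two, the futility look was ignored and the sentence claiming otherwise is false. The documents do not support that. At 29% information a conservative boundary costs almost nothing: an O'Brien-Fleming-type beta-spending rule needs 464, which is the planned number. The requirement that all key secondaries also cross lowers the loss further. The boundary is deliberately kept out of the protocol (section 19.8), so this document can neither confirm nor refute the statement. This part of the defence stands in full.

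On exclusions, the defence is that section 12.2 asks sites to keep screening, randomisation and first dose close together, that the sample size is only approximate, and that power at 2% exclusions still rounds to 90%. The first point limits the number of exclusions but does not remove them, and the same section says that a patient whose eligibility changes before dosing should not be treated. The other two bear on size, and they do keep the point modest. None of them makes 464 randomised the same as 464 analysed.

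**Conclusion.** The stated 90% is the power with all 464 randomised patients in the mITT, and so a ceiling for the primary analysis as defined in section 19.3. The margin above the fixed-sample requirement is two patients. Whatever part of it the futility look uses is not available for exclusions. The shortfall is about 1.5 points at 5% exclusions (90.1% to 88.6%) and about 3 points at 10% (90.1% to 86.9%), before any futility loss. These figures rest on assumed exclusion rates and on the plan's own success rates. The protocol does not show that the futility statement is wrong. It shows only that the statement fits a conservative boundary: z at or below about −0.9 if the primary endpoint alone decided, and a less strict one under the joint rule, depending on the correlations.

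**What to change.** In section 19.1, and in the matching synopsis entry, state that 464 randomised patients give about 90% power if all of them enter the mITT, and add the power at an assumed mITT exclusion rate, for example 88.6% at 5%. Keep the futility sentence. Confirm in the SAP, where the boundary belongs, that the chosen boundary keeps the restated power. The cost is one or two sentences and a slightly less favourable stated power. No additional patients are needed.

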### 19.2 Stratification

Randomization will be done centrally, using pre-determined schedule, and will assign subjects in a 1:1 ratio to opaganib added to standard of care or matching placebo added to standard of care.

In order to ensure balance of standard treatment regimens in both treatment arms as well as with regard to patient risk status, randomization will be determined based upon two stratification factors:

- a) Whether SoC treatment has established efficacy (yes versus no). The proven effective therapies for the purpose of this protocol will be adjusted as new data emerges and will be documented in a stand-alone document entitled Approved COVID-19 Therapies which will be updated and shared with study personnel regularly.
- b) Patients will further be stratified based on meeting three or more high risk clinical parameters for COVID-19 outcomes at baseline (yes or no).

Refer to Section 12.2 for further details.

### 19.3 Populations for Analysis

The primary analysis will be based on the modified Intent to treat population (mITT), which consists of all patients that were randomized and treated with at least one dose of study drug and who met entry criteria #3 (The patient requires, prior to first dose of study drug, high flow supplemental oxygen or positive pressure ventilation, or is receiving oxygen via a non-rebreather or reservoir mask, capable of delivering high concentrations of oxygen. Patients who require mechanical ventilation or no longer

require supplemental oxygen prior to receiving the first dose of study drug will not be included in the mITT analysis set.

The primary analysis will also be analyzed using a Per-Protocol (PP) population that will be further defined in the SAP and the Intention-to-treat (ITT) population who consists of all randomized patients. In all efficacy analyses, treatment group will be assigned per randomization assignment.

Safety analyses will be based on the safety analysis set, which consists of all patients who received at least one dose of study drug and analyzed based on the actual treatment the subject received.

